Our team is well-suited to conduct the trial. We bring together key members of the initial PTSD treatment model development team ([name] & [name]) with the investigator who took the lead on its adaptation for use in an addiction setting ([name]). Additionally, we have brought in leaders in VA on both the impact of PTSD on SUD treatment outcomes ([name]) and the effectiveness of SS in a VA addiction setting ([name]).

IV. RESEARCH DESIGN AND METHODS

A. Design

1. Overview

The proposed research will evaluate the effectiveness of the addition of a relatively simple, manual-guided CBT for PTSD to TAU in patients with co-occurring PTSD and SUD. One-hundred-sixty outpatients with comborbid PTSD/SUD will be randomly assigned to receive either CBT for PTSD in conjunction with standard TAU (n = 80) or TAU (n = 80) without additional individual treatment. Recruitment will target participants at three VA intensive outpatient addiction programs as well as participants with SUD and PTSD in those facilities who are not in the IOP. Participants will be assessed at baseline, post-treatment (approximately 4 months from baseline) and 6 month follow-up (approximately 10 months from baseline). Consistent with the goals of CBT for PTSD, the range of assessed outcomes includes both PTSD and substance use. Clinician adherence to the manual will be evaluated. Primary analyses will focus on the hypothesis that CBT for PTSD is more effective in reducing symptoms of PTSD than TAU.

2. Design considerations

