We aim to have a sample that would yield .80 power in longitudinal analysis with generalized estimating equations model (a type of generalized linear mixed models) to find a standardized detectable difference from .4 to .5 between intervention and usual care, assuming alpha = .05, two-tailed. We assume that the correlation between repeated measures will be .60. The outcome of treatments will be measured at two points in time (3-month and 9-month) for each individual. The sample size for our primary hypothesis (difference in slopes by treatments) is based on Diggle, Liang, and Zeger, who developed a formula to calculate sample size for longitudinal studies with repeated measures to estimate the difference between slopes (or rate of change in CAPS as in this case) of two groups (m = size per arm):

$$M = 2(Z_{\alpha} + Z_{\beta})^{2} \sigma^{2} (1 - \rho) / (nS_{x}^{2} d^{2})$$

where $S_x^2 = \sum_j (x_j - \bar{x})^2 / d$, the within-subject variance of the x_j ; type I error α = 0.05, power β = 0.8 and the smallest meaningful difference d = $\beta_{1B} - \beta_{1A}$ and σ^2 = $Var(\epsilon_{ij})$ measures the unexplained variability in the response, $Corr(Y_{ij}, Y_{ik}) = \rho$ for all $j \neq k$, and n is the number of repeated measures per person.

Using this formula and based on these assumptions, we estimated the sample size needed. Table 2 shows how required total enrollment (both groups) would vary for a range of expected effects and if the true effect is larger or smaller than expected for a range of possible missing data scenarios.

Table 2. Enrollment Number N (total of two groups) as a function of effect size and rates of missing endpoints due to drop out and loss to follow-up

	Loss to Measurement						
actual effect size	10%	15%	20%				
.40	160	169	180				
.45	126	134	142				
.50	102	108	115				

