Clinician Administered PTSD Scale (CAPS): The CAPS⁷⁸ is a structured diagnostic interview and is widely regarded as the gold standard for determining a diagnosis of PTSD. It has excellent reliability and validity^{78, 79} PTSD diagnosis on the CAPS is based on meeting the DSM-IV symptom criteria, as well as having a minimum severity score of 45. Symptoms are considered to be present when they have a frequency rating of at least 1 and an intensity rating of at least 2.⁷⁹ Ratings will be based on current symptoms (past month).

Structured Clinical Interview for DSM-IV-Patient Edition with Psychotic Screen (SCID-P): Substance use disorders and other Axis I psychiatric diagnoses (other than PTSD) will be established using the SCID. 80-82 The SCID is a semi-structured interview that is widely accepted as the gold standard for establishing adult psychiatric diagnosis. 82 Our research center has extensive experience training research interviewers and using the SCID with a wide range of clinical populations, including patients with co-occurring psychiatric and substance use disorders.

3. Outcomes

Participants' treatment outcomes will be assessed at baseline, post-treatment for the CBT group (approximately 3 months after baseline) and 3 months after baseline for the TAU group, and at 6 month follow up (approximately 9 months after baseline).

CAPS: PTSD severity, as measured by the CAPS (see above) will serve as the primary outcome measure. CAPS severity is calculated by summing the frequency and intensity score for each item. We will also examine the percentage of patients who show clinically significant change on the CAPS, as defined as a decrease of 10 points or more⁷⁹.

PTSD Checklist (PCL): A secondary measure of PTSD will be the PCL.⁸³ The PCL is a widely used self-report measure that assesses the 17 DSM-IV PTSD symptoms. Responses to these questions are on a scale of 1 to 5 ("not at all" to "extremely"). The PCL has excellent psychometric properties. It will be administered at all assessments, and at every other treatment session to monitor symptoms.⁸³

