Individuals providing consent and meeting inclusion/exclusion criteria as confirmed by the baseline assessment will then be randomized. We will perform block randomization (block size of 2, 4, and 6) in allocating subjects to treatments. Moreover, stratified block assignment will be used, so that each treatment group will be balanced on type of substance use (alcohol only versus drug with or without alcohol, 2 categories), whether the patient has severe PTSD (2 categories), and the site of treatment (2 sites).

Patients who are randomized to CBT for PTSD will receive 8-12 individual sessions of CBT for PTSD. These sessions will be offered once or twice per week depending on patient and therapist availability. All participants will receive TAU. For patients assigned to CBT, approximately one week after the end of treatment patients will be given the post-treatment assessment. Patients in TAU will be assessed 4-5 months after the baseline. Six months from the post assessments all participants will receive the 6 month follow-up assessment. Assessors will be blind to treatment condition. Patients will be paid \$30 for the post-treatment and follow up assessments. Patients will receive a reminder letter about their first appointment (and about subsequent appointments if requested.) Patients who miss a session of treatment or assessment may be sent a letter of contact, if study staff are unable to reach them by phone.

G. Data Analysis

This study is designed as a two-arm, parallel comparison of two therapies in the treatment of PTSD in patients who are receiving care in a VA intensive outpatient program for substance abuse or patients with comorbid substance use and PTSD. In designing this study, there are analysis issues that require special attention, such as handling of missing data, adjustment for loss-to-follow-up, and serial correlation for sample size calculation. The strategy for data analysis flows from the goals of the study, and in turn defines the statistical tests and sample size projections.

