Several steps will be taken in preparation for performing the primary analyses. We will evaluate the effectiveness of randomization by comparing CBT and TAU groups on demographics, baseline measures of key outcomes, and other important covariates such as psychotropic medication usage. Next we will perform simple end-point analyses of post-treatment and 6-month outcomes using t-tests (chi-square test for retention proportion) and use multiple linear and logistic regression models to examine predictors of outcome. Demographic variables, baseline severity, and medical and psychiatric comorbidities will be considered as possible covariates. Only covariates that significantly reduce variance will be added to the model.

Because the groups are randomized to be equivalent at baseline, the t-tests and end-point linear regression or logistic regression analyses are valid methods of comparison; however, patients who fail to provide any outcome data (at post-treatment and 6-months) measurement will naturally get excluded from the analyses, and this may introduce bias in the estimates. Furthermore, end-point analyses do not take into account the longitudinal nature of the data, time-varying covariates, or correlations among repeated observations.

For our main analysis, we will perform both cross-sectional and longitudinal analyses using Generalized Linear Mixed Model (SAS PROC MIXED) for continuous outcomes (for example, primary hypothesis) and PROC GLIMMIX for binary outcomes. We will model changes over time at population level. We will examine the

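### The post-treatment visit is set by end of therapy in the CBT arm and by the calendar in the TAU arm, so the arms may be compared at different times since baseline

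*Combined protocol and SAP*

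**What the plan says.** Section IV.F (Procedure) ties the CBT visit to an event: "For patients assigned to CBT, approximately one week after the end of treatment patients will be given the post-treatment assessment". It ties the TAU visit to the calendar: "Patients in TAU will be assessed 4-5 months after the baseline". Follow-up then runs from each patient's own post visit: "Six months from the post assessments all participants will receive the 6 month follow-up assessment". The course is 8-12 sessions, and "These sessions will be offered once or twice per week depending on patient and therapist availability".

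Other sections give one time for both arms, but do not agree with each other:

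- IV.E.3 (Outcomes): "post-treatment for the CBT group (approximately 3 months after baseline) and 3 months after baseline for the TAU group", with follow-up at about 9 months.
- IV.B.6 (Power analysis): "The outcome of treatments will be measured at two points in time (3-month and 9-month) for each individual".
- IV.A.1 (Overview): about 4 months for post-treatment and about 10 months for follow-up, for all participants.

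IV.G.1 plans end-point t-tests at each visit. It argues from randomisation that "the t-tests and end-point linear regression or logistic regression analyses are valid methods of comparison". It then plans a mixed model with a linear, or possibly quadratic, time trend by group, and does not say whether time is actual or nominal. No section sets a visit window, or defines end of treatment for CBT patients who stop early.

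**The concern.** Randomisation makes the arms comparable at the same time since baseline. It does not make one arm at 9 weeks comparable with the other at 19 weeks. Both arms receive addiction treatment, so CAPS may move in both. In the pilot trial it fell in both arms, though with only 8 and 4 patients and a significant fall only under CBT. If the mean is still changing, an end-point test takes in the timing gap as if it were a treatment effect. A slope test on actual times escapes this only if the assumed time trend has the right shape.

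Three lesser consequences follow.

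- The Time-line Follow-back covers 90 days and is a secondary measure for Hypothesis 2. At the post-treatment visit of a CBT patient seen before day 90 it would reach back before baseline.
- In the pilots 31-35% of CBT patients stopped before session 8. For such patients IV.F leaves the visit date undefined, although the analysis is intention-to-treat.
- The baseline assessor is, where possible, also the follow-up assessor (IV.E.5). The interval could hint at the arm, but nothing in the documents shows that it does.

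**Working it through.** **Visit times implied by IV.F.** CBT visit = sessions / weekly frequency + 1 week, without delays:

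- 8 sessions twice weekly: 4 + 1 = 5 weeks (1.15 months)
- 12 twice weekly: 6 + 1 = 7 weeks (1.61 months)
- 8 weekly: 8 + 1 = 9 weeks (2.07 months)
- 12 weekly: 12 + 1 = 13 weeks (2.99 months)

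TAU at 4-5 months is 17.4-21.7 weeks. The gap runs from 4 - 2.99 = 1.0 month to 5 - 1.15 = 3.85 months. It carries forward to follow-up.

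**Inputs.** From IV.B.6: alpha 0.05 two-sided, correlation 0.6, d = 0.4, and 80 per arm less 10% = 72. Assumed: SD 20 (pilot baseline SDs 13.9-23.5), compound symmetry, no treatment effect, and the same mean CAPS curve f(t) in both arms. The documents give no trajectory, so the curves are assumptions too.

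**Formulas.** CBT is seen at 0, c, c+6 months and TAU at 0, a, a+6. The false end-point difference is f(c) - f(a), with SE = 20 × √(2/72) = 3.33. The slope test uses the generalised least squares group-by-time coefficient on actual times. The quadratic test is a joint 2-df test of group-by-time and group-by-time². That joint test is my choice; the plan writes the quadratic model but names no test for it.

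Example, f(t) = -20(1 - e^(-t/3)), c = 3, a = 4.5: f(3) = -12.64 and f(4.5) = -15.54. The difference is 2.9 points against CBT, z = 2.9/3.33 = 0.87, and the t-test rejects 14% of the time.

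**CBT at 3 months, TAU at 4-4.5 months**

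| Common curve | Post-treatment difference | t-test rejects | Linear slope test rejects |
|---|---|---|---|
| 20-point decline levelling off, time constant 1-3 months | 0.6-2.9 against CBT | 5-14% | 6-9%, towards CBT |
| Linear decline, 2 points/month | 2.0-3.0 against CBT | 9-15% | 5% |
| 20-point fall by 2 months, half lost by 10.5 months | 1.2-1.8 towards CBT | 6-8% | 6-7% |

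Against 0.4 × 20 = 8 points, 0.6-2.9 is 8-36%. The difference at follow-up is 0-0.4 points under levelling-off. Under the other two curves it equals the post-treatment difference. A baseline-to-post contrast of group means, which IV.G.1 also describes, has SE = √(2 × 400 × 0.8/72) = 2.98 and rejects 5.5-16% under levelling-off. The quadratic test under levelling-off rejects 8-12%, 17-29% and 43-70% for time constants of 3, 2 and 1 months.

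**Other timings, levelling-off curve**

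- CBT 3 months, TAU 5: 0.9-3.6 points, slope test 9-12%.
- CBT 9 weeks, TAU 4.5 months: 2.3-5.6 points, slope test 10-18%.
- CBT spread over 9-17 weeks, TAU over 4-5 months: 0.9-3.0 points, slope test 7-9%.
- CBT 4 months, TAU 4-4.5: 0-0.8 points, slope test 5%.
- Any common time: bias 0 and rejection 5%, under every curve.

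**If the model uses nominal times** (0, 4, 10) with TAU seen at 4.5 months, SD 25 and a linear fall of 1 point/month, the slope test rejects 6.6% with CBT at 2.99 months and 13.3% with CBT at 1.15 months.

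**Time-line Follow-back.** Pre-baseline days = max(0, 90 - 7 × weeks). For CBT at 5, 7, 9 and 13 weeks this is 55, 41, 27 and 0 of 90. For TAU it is 0.

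**Early stoppers.** 80 × (1 - 0.692) = 25 and 80 × (1 - 0.65) = 28 of the 80 CBT patients, projected from very small pilots.

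**The case against.** The strongest reply is that the conflict may be small in practice. TAU at 4-5 months overlaps the Overview's 4 months, and 12 weekly sessions plus a week matches the 3 months in IV.E.3. No single section schedules CBT at 3 months with TAU at 4-4.5. Missed sessions and limited staff time may push CBT towards 4 months, where the bias is under 1 point for a levelling-off decline. This stands as a limit on size. It does not reconcile TAU at 4-5 months with TAU at 3 months, and CBT at 3 months is what IV.F itself implies for 12 weekly sessions.

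Second, the primary hypothesis in Section I refers to the conclusion of treatment, so an end-of-treatment visit serves the stated question. That is fair, and Section I belongs among the texts to reconcile. But TAU has no matching end of treatment, so the comparison still needs a common clock.

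Third, the t-tests are preparatory, the bias mostly runs against CBT, and the quadratic rates rest on a test the plan does not name. All true, and the highest quadratic rates need a very fast early decline, so they should carry little weight. The linear slope test, which the plan does name, leans towards CBT under levelling-off. Two planned analyses could therefore disagree for scheduling reasons alone.

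**Conclusion.** The concern holds. The contradiction between sections is certain from the text. Bias is possible rather than certain: its size and direction depend on how CAPS moves without a treatment effect and on how quickly CBT is delivered, and the documents fix neither. Under the assumptions above, a gap of 1-1.5 months gives false post-treatment differences of about 0.6-3.0 points in either direction and a slope-test error of 5-9%. Faster CBT delivery makes both larger. The bias vanishes if CAPS is stable over the interval. It also vanishes in the model if actual times are used and the trend has the right shape. The end-point tests cannot be called valid on randomisation alone under this schedule. This should be fixed, although it would not necessarily overturn a result.

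**What to change.** Reconcile Sections I, IV.A.1, IV.B.6, IV.E.3 and IV.F to one assessment time after randomisation, with the same window in both arms, at least 90 days after baseline, and kept regardless of when CBT sessions end or stop. Take follow-up a fixed six months later. The Overview's 4 and 10 months would serve: 4 months lies in the present TAU window and leaves 17.4 - 13 = about 4 weeks' slack after 12 weekly sessions plus one week. State that the model uses actual time.

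The cost is wording in the protocol and operations manual; visits and staff do not change. Nor does the sample size: Table 2's 160 is reproduced by a time-averaged formula with three measures and no visit times, 2 × (1.96 + 0.842)² × (1 + 2 × 0.6)/(3 × 0.4²) = 71.95 per arm, and 2 × 71.95/0.9 = 159.9. There is a real downside. The fastest completers (last session about week 4) would be seen about 13 weeks after it, those with 8 weekly sessions about 9 weeks after, and patients delayed beyond the slack would be seen before therapy ends.

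If data are already collected, report days from baseline to each visit by arm, count only post-baseline Time-line Follow-back days, and show CAPS results with visit as a category and with linear and quadratic time. Say plainly that the categorical analysis carries the same bias as the t-test, that where visit times do not overlap any adjustment for actual time is extrapolation, and that agreement among the three is not proof of validity.

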The development of a model of integrated treatment for Veterans with PTSD and substance use disorders would represent a significant advance in the healthcare being provided to Veterans. Historically addiction treatment programs have not addressed PTSD out of concern that targeting the PTSD would exacerbate reexperiencing symptoms and jeopardize early and unstable periods of abstinence. ^{18, 19} The opposite argument has also been proposed. Evidence in support of the self-medication theory indicates that people use substances as a means to control their re-experiencing symptoms. ^{20, 21} Therefore ignoring the PTSD may lead to increased relapse and poorer outcome. Integrating PTSD treatment into an addiction setting could result in improved PTSD and substance use outcomes as well as improved physical health and functioning. ¹³

We propose to conduct a randomized clinical trial to evaluate the effectiveness of a relatively simple, manual-guided cognitive behavioral therapy (CBT) for PTSD in patients with SUD. One hundred sixty outpatients with comborbid PTSD and SUD will be randomly assigned to receive either: CBT for PTSD in conjunction with standard treatment as usual (TAU) (n = 80) or TAU only (n = 80) without additional individual treatment.

Our hypotheses are as follows:

Primary Hypothesis

1. Patients who receive CBT will have greater improvements in PTSD symptom severity relative to patients who receive TAU only at both the conclusion of treatment and at the 6-month follow-up.

Secondary Hypotheses

- 2. Patients who receive CBT will have greater reductions in substance use severity (drugs and/or alcohol) than patients who receive TAU only at both the conclusion of treatment and at the 6-month follow-up.
- 3. Patients in the CBT condition will have better retention in the addiction treatment program relative to patients who receive TAU only.

Typically patients with co-morbid PTSD/SUD are required to have their SUD "under control" before they are referred for PTSD treatment. This puts these patients in a symptomatic "Catch-22:" If they stop using substances PTSD symptoms worsen, if they only try to address PTSD without clinical attention to their substance use disorder, their substance use worsens.

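### One week after CBT ends, the past-month CAPS mostly scores days during therapy, while TAU is scored at 4-5 months; this may dilute the post-treatment contrast

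*Combined protocol and SAP*

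**What the plan says.** **Target and instrument.** The primary hypothesis (Section I) claims greater improvement with CBT "at both the conclusion of treatment and at the 6-month follow-up". Under Outcomes (Section IV.E.3), "PTSD severity, as measured by the CAPS (see above) will serve as the primary outcome measure". That cross-reference leads to the CAPS description under Eligibility (Section IV.E.2): "Ratings will be based on current symptoms (past month". No different recall period is given for the later visits.

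**Timing under Procedure (Section IV.F).** In the CBT arm: "For patients assigned to CBT, approximately one week after the end of treatment patients will be given the post-treatment assessment". In the control arm: "Patients in TAU will be assessed 4-5 months after the baseline". The same section allows 8 to 12 CBT sessions, once or twice a week, and counts the 6-month follow-up from the post-treatment assessment.

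**Timing elsewhere.** Section IV.E.3 has "post-treatment for the CBT group (approximately 3 months after baseline" and also puts the TAU assessment at 3 months. The design overview (Section IV.A.1) has "Participants will be assessed at baseline, post-treatment (approximately 4 months from baseline) and 6 month follow-up (approximately 10 months from baseline". The power section (IV.B.6) uses 3 and 9 months. The three timings of the post-treatment visit are not reconciled.

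**The concern.** A past-month rating made one week after the last session is mainly a rating of the therapy period. The post-treatment visit is a named time point of the primary hypothesis. It has its own t-test (Section IV.G.1), and it enters the planned contrast of group means across time points. If symptoms are still falling in the last weeks of therapy, the CAPS at this visit averages partly treated days with fully treated ones.

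Only the CBT arm is exposed, because Section IV.F sees TAU much later. The two arms are then compared at different distances from baseline as well as over differently placed windows. At stake is an understated contrast at the first visit, which could look like delayed benefit when the follow-up visit is set beside it.

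**Working it through.** **Inputs.** Recall window: one month, taken as 30 days (IV.E.2). Gap from last session to visit: 7 days (IV.F). Sessions: 8 to 12, at 1 or 2 per week (IV.F). Assumptions: session 1 at baseline, evenly spaced sessions, and equal weight for each day in the rating. The plan states no figure for the overlap, so there is none to reproduce.

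**Step 1, overlap.** Scored days before the last session = 30 − 7 = 23, and 23/30 = 77%. With a month of 28-31 days and a gap of 5-10 days, the range is 28 − 10 = 18 to 31 − 5 = 26 days.

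**Step 2, visit dates.** The last session falls on day T = (sessions − 1) × 7 / (sessions per week). The visit is on day T + 7 and the window opens on day T − 23.

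**Step 3, share of the end-of-treatment effect captured.** Two assumed courses for the CBT-TAU difference:

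- Straight line from session 1 to the last session, then flat: share = 1 − 23²/(2 × 30 × T) = 1 − 529/(60T).
- Straight line to a full effect at M = T/2, then flat: share = 1 − (M − o)²/(2 × 30 × M), where o = T − 23 is the opening day; the share is 100% if o ≥ M.

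| Course | T | Visit day | Window opens | Straight line | Complete by mid-therapy |
|---|---|---|---|---|---|
| 8 sessions, twice weekly | 24.5 | 31.5 | 1.5 | 64% | 84% |
| 12 sessions, twice weekly | 38.5 | 45.5 | 15.5 | 77% | 99% |
| 8 sessions, weekly | 49 | 56 | 26 | 82% | 100% |
| 12 sessions, weekly | 77 | 84 | 54 | 89% | 100% |

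If benefit began only at session 4, the shares would be 47%, 69%, 69% and 84%. Nothing in the documents selects among these courses.

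**Step 4, other visit dates.** At 3 months (day 91) the window opens on day 61. Courses ending on day 24.5, 38.5 or 49 have no overlap; 12 weekly sessions have 77 − 61 = 16 of 30 days. The straight-line share there is 1 − 16²/(2 × 77 × 30) = 94.5%. At 4 months (day 122) the window opens on day 92. No course overlaps, and the longest can start 92 − 77 = 15 days after baseline before it does.

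**Step 5, the linear-trend model (IV.G.1).** With visits at 0, 3 and 9 months the mean time is 4, the deviations are −4, −1 and +5, and their squares sum to 42. With no difference at baseline and complete data, the slope difference is (5δ₂ − δ₁)/42, where δ₁ and δ₂ are the arm differences at the two visits. If both equal δ, this is 4δ/42. If δ₁ is cut to 0.64δ, it is 4.36δ/42. Dilution at the middle visit does not shrink this parameter.

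**Step 6, follow-up visit.** Under IV.F the CBT follow-up falls at about day 31.5 + 183 = 214.5 to 84 + 183 = 267. Its window is well clear of therapy. TAU follow-up falls at 10-11 months, so the unequal dates carry through to that visit.

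**The case against.** The strongest reply is that this is mostly the unequal visit timing seen from another side. That largely stands. With a common 3-month date, three of the four courses lose nothing and the fourth keeps 94.5% under the straight-line course. The recall window's own contribution at a common date is then 0 to about 6%. It mainly gives a reason to prefer 4 months to 3.

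The 64% figure also needs 8 sessions in 24.5 days. If the one-week visit coincided with 3 or 4 months, the last session would fall near day 84 or 115, and the straight-line share would be 1 − 529/5040 = 90% or 1 − 529/6900 = 92%. That stands too, but IV.F permits the short course.

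A reader might draw four stronger conclusions that the documents do not support:

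- *That the effect is understated as a matter of fact.* No symptom trajectory is given, and weekly courses lose nothing if benefit is complete by mid-therapy.
- *That the 10-point CAPS difference in Section IV.G.1 should be discounted.* That figure is for the end of the study, where the window is clear of therapy.
- *That drop-outs are rated on pre-therapy days.* Read literally, a last session on day 7, 14 or 21 puts 16, 9 or 2 such days in the window. But the plan does not say when patients who stop before 8 sessions are assessed; at a fixed 3 or 4 months there would be none. The pilots' non-completion rates (35% and 30.8%, from completion of 65% and 69.2%) do not show how early those patients stopped.
- *That power for the primary analysis falls by a known amount.* The stated primary interest is the slope, which Step 5 shows is not shrunk. Nothing says that the planned d = .40 is a day-specific effect rather than the difference in CAPS as rated.

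**Conclusion.** The point holds as a possible dilution of the post-treatment contrast, combined with unequal timing between the arms. The firm part is that, on the Section IV.F schedule, about 23 of 30 scored days (18-26) in the CBT arm precede the last session, and CBT is rated at about day 32-84 against 4-5 months for TAU. The size is conditional: 64-89% of the end-of-treatment effect captured under a straight-line course, 84-100% if benefit is complete by mid-therapy. Both rest on equal weighting of days and a start at baseline; if raters or patients give more weight to recent days, the loss is smaller. The matter is confined to the t-test and mean contrast at the first outcome visit. It is worth correcting because the protocol already contains a date that removes the overlap for courses starting near baseline.

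**What to change.** Reconcile Sections IV.A.1, IV.E.3 and IV.F on one post-treatment date counted from baseline, the same in both arms: about 4 months, the date already in IV.A.1. Apply it whatever number of sessions was attended, which also settles the timing for patients who stop early. Time the 6-month follow-up from it, at about 10 months, and bring the 3- and 9-month times in IV.B.6 into line. State in IV.E.3 that the past-month recall applies at every visit.

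A common 3-month date would repair the unequal timing but leave up to 16 of 30 scored days in therapy for 12 weekly sessions. A minimum interval after the last session should not be added, because it would make visit timing depend on arm again whenever a course starts late or runs long.

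The change is to wording only; it needs no extra visit, staff or instrument and leaves treatment delivery alone. Its cost is that, for courses starting at baseline, CBT patients are first assessed 122 − 77 = 45 to 122 − 24.5 = 97.5 days after their last session instead of about 7. The visit then measures the result some weeks after therapy rather than on finishing it, so the hypothesis wording should say so. There is also slightly more time for loss to follow-up, and a course that starts more than about two weeks late or runs long could still overlap the window.
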